5.4.4 Sensitivity/Supplementary Analyses for Efficacy Endpoints

SENSITIVITY ANALYSES BASED ON DIFFERENT POPULATIONS

Sensitivity analyses of tumor response will be performed using the data from all HCC-1L subjects (N=100; referred to as “Sensitivity Analysis 1”), as well as the data from the first 60

HCC-1L subjects (N=60; referred to as “Sensitivity Analysis 2”), as mentioned above in the beginning of [Section 5](#) and [5.2.1](#).

SUPPLEMENTARY ANALYSIS BASED ON DIFFERENT DERIVATION RULE

Supplementary analysis of tumor response using the different derivation rule for the situation with more than one missed visit/tumor assessment will also be provided for the first 80 HCC-1L subjects (referred to as “Supplementary Analysis”), following the censoring rule for supplementary analysis described in [Section 8.2](#).

5.4.5 Analyses of Concordance between Independent Imaging Review and Investigator per mRECIST

Concordance on BOR per mRECIST for each subject between assessment by IIR and by investigator will be presented for the first 80 HCC-1L subjects using cross-tabulation table.

5.5 Pharmacokinetic, Pharmacodynamic, Pharmacogenomic, and Other Biomarker Analyses

The details of the pharmacokinetic analyses plan and results will be provided in a separate report or subsequent CSR, once they become available.

5.5.1 Pharmacokinetic Analyses

Pharmacokinetic analyses will be performed in the DLT evaluation part and the expansion part. The Safety Analysis Set will be used for individual lenvatinib plasma concentrations and pembrolizumab serum concentrations listings. The PK Analysis Set will be used for the summaries of lenvatinib plasma concentrations and pembrolizumab serum concentrations, for summaries and listings of PK parameters of lenvatinib and for listings of ADA levels.

5.5.1.1 Plasma or Serum Concentration and its PK Parameter Analysis

Concentration

Plasma concentration values for lenvatinib and serum concentration values for pembrolizumab will be summarized using descriptive statistics (n, mean, standard deviation [SD], median, minimum [min] and maximum [max]) by nominal time point by lenvatinib starting dose group.

Plasma concentrations of lenvatinib, serum concentrations of pembrolizumab and ADA levels will be listed for each subject by actual sampling time by lenvatinib starting dose group.

PK Parameter

PK parameters will be derived by non-compartmental analysis using WinNonlin software (version 6.2.1 or later) according to 302-104.00-MNL.

The following pharmacokinetic parameters for lenvatinib will also be calculated using noncompartmental analysis: C_{max} , t_{max} , $AUC_{(0-t)}$, $AUC_{(0-ti)}$, $AUC_{(0-inf)}$, $t_{1/2}$, CL/F , V_z/F , $C_{ss,max}$, $C_{ss,min}$, $t_{ss,max}$, $AUC_{(0-\tau)}$, CL_{ss}/F , $C_{ss,av}$, $R_{ac}(C_{max})$, $R_{ac}(AUC)$, PTF ratio.

Other PK parameters may be calculated as appropriate.

Descriptive statistics will be tabulated for the PK parameters of lenvatinib by lenvatinib starting dose group. Descriptive statistics (n, mean, SD, median, min, and max) will be presented for all parameters (apart from t_{max} where mean and SD are not required). In addition, geometric mean and %CV will also be presented for all parameters apart from t_{max} .

PK parameters of lenvatinib for each subject will be listed.

5.5.1.2 Pharmacokinetic Data Figures

Linear and semi-log plots of each subject's lenvatinib plasma and pembrolizumab serum concentration data vs actual time will be displayed by lenvatinib starting dose group. The actual time will be plotted on the X-axis and the concentrations of lenvatinib and pembrolizumab will be plotted on the Y-axis.

The linear and semi-log mean (+SD) plots of lenvatinib plasma concentration versus nominal time will be displayed. The nominal time will be plotted on the X-axis and the mean (+SD) will be plotted on the Y-axis on the same graph by lenvatinib starting dose group by visit (Cycle 1 Day 1 and Cycle1 Day 15).

The linear and semi-log mean (+SD) plots of pembrolizumab serum concentration versus nominal time will be displayed by lenvatinib starting dose group. The nominal time will be plotted on the X-axis and the mean (+SD) will be plotted on the Y-axis on the same graph by visit (Cycle 1 Day 1 and Cycle1 Day 15).

Box plots, with individual sparse PK data, will also be displayed by lenvatinib starting dose group for both lenvatinib and pembrolizumab.

5.6 Safety Analyses

All tolerability analyses will be performed on the DLT Analysis Set. Safety analysis will be performed based on the Safety Analysis Set. Safety data will be presented with the format as mentioned above in the beginning of [Section 5](#) and [5.2.1](#) by using summary statistics (eg, n, mean, standard deviation, median, Q1, Q3, minimum, maximum for continuous variables; number [percentage] for categorical variables). Safety data by lenvatinib starting dose (ie, 8 mg, 12 mg) will also be presented in all HCC-1L subjects, using overview table of AE, and additional tables if deemed necessary.

5.6.1 Extent of Exposure

The parameters for extent of exposure will be computed for combination (lenvatinib plus pembrolizumab), lenvatinib alone and pembrolizumab alone, respectively. The parameters to be derived are defined as follows:

1. Number of administrations of pembrolizumab = Total number of IV administrations.
2. Duration of treatment (days) = Last dosing date – first dosing date + 1
3. Duration of treatment (months) = (Last dosing date – first dosing date + 1) / (365.25/12)
4. Total doses (mg) of lenvatinib = Sum of all the actual dose
5. Dose intensity of lenvatinib (mg / (days)) = Total doses / Duration of treatment
6. Received dose as percentage of planned starting dose per subject (%) = $100 \times \text{Dose intensity} / \text{Planned starting dose}$

The last dosing date should be the date received non 0 (zero) mg dose. The following table provide the parameters to be summarized for the study drug.

Lenbatinib plus Pembrolizumab	Lenvatinib	Pembrolizumab
3*	3, 4, 5**, 6	1, 3
*: defined as the duration between the earliest first dose start date of either medication and the latest last dose end date of either medication	** : presented by starting dose (8 mg, 12 mg)	

Furthermore, the following information of administration will also be summarized for lenvatinib only.

The number (percentage) of subjects who experienced dose reductions and treatment interruptions will be summarized based on actual dose records from study medication data. The number (percentage) of subjects with dose reduction, interruption by period (eg, every 3 weeks) will also be summarized based on their time of first dose reduction, interruption, respectively.

Time (weeks) to first dose reduction and to first dose interruption of lenvatinib will be summarized by descriptive statistics for subjects with a dose reduction/interruption event.

Frequency of dose interruptions will also be summarized by appropriate categories (eg, 1, 2, 3, ≥ 4).

Frequency of dose reductions will be summarized by categories (1, 2, 3, 4).

- Definition of Dose Reduction of lenvatinib:
 - Dose level reduces from previous dose level after dose interruption period per Protocol Section 9.4.1.3.2 Table 3. For example, 12 mg followed by 0 mg, followed by 8 mg; 8 mg followed by 0 mg and then followed by 4 mg.
- Definition of Dose interruption of lenvatinib:
 - Only include the scenario that the before and after dose 0 mg (interruption period), the dose levels are the same. For example: 12 mg followed by 0 mg and followed by 12 mg; 8 mg followed by 0 mg, then followed by 8 mg.
 - If dose level reduces from previous dose level after dose interruption period (dose 0), it should be counted as dose reduction, but not dose interruption. For example, 12 mg followed by 0 mg followed by 8 mg, the period with 0 mg should not be counted as dose interruption, instead it should be counted as a dose reduction.
Note that change from 4 mg QD to 4 mg QOD is also considered as dose reduction.
 - If after dose 0 mg, the subject discontinued from treatment permanently, it should be counted as a treatment discontinuation instead of a dose interruption.

Subject data listings will be provided.

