5.6.3 Adverse Events

The AE verbatim descriptions (investigator terms from the CRF) will be classified into standardized medical terminology using the MedDRA (version 22.1). Adverse events will be coded to the MedDRA lower level term (LLT) closest to the verbatim term. The linked MedDRA PT and SOC will also be captured in the database.

Only treatment-emergent adverse events (TEAEs), defined in [Section 8.1](#), will be included in summary tables. All AEs, treatment emergent or otherwise, will be presented in subject data listings.

MedDRA preferred terms ‘Neoplasm Progression’, ‘Malignant Neoplasm Progression’ and ‘Disease Progression’ will be excluded from TEAE summary tables, if not related to the study drug.

A subject will be counted only once within a SOC and PT, even if the subject experienced more than 1 TEAE within a specific SOC and PT.

An overview table, including the incidence of and the number of subjects with TEAEs, treatment-related TEAEs, TEAEs/treatment-related TEAEs with worst CTCAE grade 3 or above, treatment-emergent serious adverse events (SAEs), deaths, and TEAEs that led to treatment discontinuation of lenvatinib, pembrolizumab, or both, dose reduction of lenvatinib, or dose interruption of lenvatinib, pembrolizumab, or both will be provided.

The incidence of the following events will be reported as the number (percentage) of subjects with TEAEs by MedDRA SOC and PT:

- TEAEs
- TEAEs by worst CTCAE grade
- TEAEs with worst CTCAE grade 3 or above
- TEAEs with any CTCAE grade 3 or 4
- Treatment-emergent SAEs
- Fatal TEAE
- Non-fatal treatment-emergent SAEs
- Treatment-related TEAEs
- Treatment-related TEAEs by CTCAE grade
- Treatment-related TEAEs with worst CTCAE grade 3 or above
- Treatment-related TEAEs with any CTCAE grade 3 or 4
- Treatment-related treatment-emergent SAEs
- Treatment-related Fatal TEAE
- TEAEs leading to discontinuation of lenvatinib
- TEAEs leading to dose reduction of lenvatinib
- TEAEs leading to dose interruption of lenvatinib
- TEAEs leading to dose modification (reduction/interruption) of lenvatinib
- TEAEs leading to discontinuation of pembrolizumab
- TEAEs leading to dose interruption of pembrolizumab
- TEAEs leading to discontinuation of both lenvatinib and pembrolizumab
- TEAEs leading to dose interruption of both lenvatinib and pembrolizumab

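### Section 5.6.1 counts a lenvatinib mg-level reduction only after a 0 mg period, so a direct step-down is counted as neither reduction nor interruption

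*SAP*

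**What the plan says.** SAP Section 5.6.1 summarises lenvatinib reductions and interruptions in four ways: the share of subjects affected, the share by period of first occurrence, the time to first occurrence, and the number of occurrences per subject. The source is what was recorded as taken; the share of subjects "will be summarized based on actual dose records from study medication data".

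The definitions are:

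- Reduction: "Dose level reduces from previous dose level after dose interruption period per Protocol Section 9.4.1.3.2 Table 3". Both examples pass through zero: "For example, 12 mg followed by 0 mg, followed by 8 mg; 8 mg followed by 0 mg and then followed by 4 mg".
- Interruption: "Only include the scenario that the before and after dose 0 mg (interruption period), the dose levels are the same".
- Precedence: "If dose level reduces from previous dose level after dose interruption period (dose 0), it should be counted as dose reduction, but not dose interruption".
- Schedule change: "Note that change from 4 mg QD to 4 mg QOD is also considered as dose reduction".
- Permanent stop: "If after dose 0 mg, the subject discontinued from treatment permanently, it should be counted as a treatment discontinuation instead of a dose interruption".

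Section 8.3 refers the reader back to Section 5.6.1 for the exposure derivations, so no other section of the SAP widens these definitions.

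**The concern.** The reduction definition has two parts: the level goes down, and it does so after an interruption. A subject who moves straight from 12 mg to 8 mg meets the first part but not the second. That subject does not fit the interruption definition either, because there is no 0 mg period and the levels differ. A real decrease in dose then appears in neither row.

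All four summaries are exposed. A subject whose only decrease is direct drops out of the reduction count, and also out of the time-to-first summary, which covers only subjects with an event. A subject who first steps down directly and later steps down through a hold is dated at the later step, placed in a later period, and counted one reduction short. The error in the counts runs one way: reductions are understated.

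**Working it through.** There is no figure in the plan to reproduce, because this is a classification rule. The check applies the literal rules of Section 5.6.1 to dose sequences and compares them with a rule that counts any decrease from the previous non-zero level.

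| Recorded sequence | Reductions, as written | Interruptions, as written | Reductions, any decrease |
|---|---|---|---|
| 12 – 0 – 8 mg | 1 | 0 | 1 |
| 12 – 0 – 12 mg | 0 | 1 | 0 |
| 12 – 8 mg | 0 | 0 | 1 |
| 12 – 8 – 4 mg | 0 | 0 | 2 |
| 12 – 8 – 0 – 4 mg | 1, dated at the 4 mg step | 0 | 2, first dated at the 8 mg step |
| 4 mg QD – 4 mg QOD | 1, through the note | 0 | 1 |

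The first two rows and the last behave as intended. The three rows with a direct mg step do not.

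**Size.** If R subjects have at least one reduction and a fraction d of them have only direct steps, the table shows R × (1 − d). The SAP gives neither R nor d. Purely as an assumption, with R = 50 among the 100 first-line subjects and d = 10%, 20% or 40%:

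- 50 × 0.90 = 45
- 50 × 0.80 = 40
- 50 × 0.60 = 30

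These figures show how the rule works; they are not estimates. If d = 0, nothing is lost.

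**QOD off-days.** The SAP does not say how a day off under QOD dosing is recorded, so there are two cases. Take 21 days (one cycle, Section 3.2) starting on a dosing day. Doses fall on days 1, 3, …, 21 (11 days) and off-days on days 2, 4, …, 20 (10 days).

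- If off-days are recorded as 0 mg, each has 4 mg QOD on both sides and fits the interruption wording. That gives 10 interruptions, and the fourth off-day is day 8.
- If 4 mg QOD is one continuous record, there are 0 interruptions.

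**The case against.** The strongest defence is that the definition follows Protocol Section 9.4.1.3.2 Table 3, which is not at hand. If that table requires a hold before every reduction, the SAP wording mirrors it and direct steps would be rare departures. Detailed derivations are also left to separate programming documents (Section 9). This limits the likely size but does not close the gap. The summary is built on doses actually taken, and a counting rule has to place every sequence that can occur. The authors wrote a note for the QD-to-QOD change and none for a direct mg step.

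Four stronger readings are tempting, and the SAP does not support them:

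- *No reduction ever counts without a 0 mg period.* The QD-to-QOD note requires none.
- *Planned QOD off-days are counted as interruptions.* This depends on record-keeping that the SAP does not describe. The text equates 0 mg with an interruption period and treats QOD as a reduced level, and an off-day lies within one such level. Only the lack of an explicit exclusion can be said.
- *The exposure and adverse event tables contradict each other.* Section 5.6.3 tabulates "TEAEs leading to dose reduction of lenvatinib", which are events attributed to an adverse event. Section 5.6.1 counts changes in dose records. The two quantities differ and need not agree under any definition.
- *The tolerability conclusion is at risk.* Sections 5.2.1 and 5.6 judge tolerability on the DLT Analysis Set. Section 5.6.1 is descriptive, and only dose intensity is marked there for display by starting dose.

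**Conclusion.** The gap is real and narrow. As written, a direct mg-level step-down in lenvatinib is counted as neither a reduction nor an interruption. This can understate the number of subjects reduced and the number of reductions, and can misdate the first one. The size is unknown and depends on how often direct steps appear in the dose records; it is zero if every mg-level decrease passed through a recorded 0 mg period.

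Total dose, dose intensity and received dose as a percentage of the planned starting dose are computed from doses taken, so they still reflect a direct step. The DLT and adverse event results do not use the definition. The QOD point is only a conditional safeguard: 0 or 10 spurious interruptions per 21 days, according to how off-days are recorded.

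**What to change.** In Section 5.6.1, for counting purposes only:

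1. Define a lenvatinib reduction as any decrease from the previous non-zero dose level, including QD to QOD, with or without an intervening 0 mg period, dated at the first dose at the lower level. Keep the existing rule that a lower level after 0 mg is not also an interruption.
2. Apply this to all four summaries: share of subjects, by period, time to first, and frequency.
3. If QOD off-days are recorded as 0 mg, state that these scheduled days are not interruptions.

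The cost is a few words and a programming change on existing dose records. The reported reduction rate may be slightly higher. No dose, schedule or clinical rule is altered.

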5.6.2 Dose Limiting Toxicity

The number (percentage) of subjects who experienced any DLT will be summarized. The category of DLT will also be summarized.

Subject data listings will be provided.

5.6.3 Adverse Events

The AE verbatim descriptions (investigator terms from the CRF) will be classified into standardized medical terminology using the MedDRA (version 22.1). Adverse events will be coded to the MedDRA lower level term (LLT) closest to the verbatim term. The linked MedDRA PT and SOC will also be captured in the database.

Only treatment-emergent adverse events (TEAEs), defined in [Section 8.1](#), will be included in summary tables. All AEs, treatment emergent or otherwise, will be presented in subject data listings.

MedDRA preferred terms ‘Neoplasm Progression’, ‘Malignant Neoplasm Progression’ and ‘Disease Progression’ will be excluded from TEAE summary tables, if not related to the study drug.

A subject will be counted only once within a SOC and PT, even if the subject experienced more than 1 TEAE within a specific SOC and PT.

An overview table, including the incidence of and the number of subjects with TEAEs, treatment-related TEAEs, TEAEs/treatment-related TEAEs with worst CTCAE grade 3 or above, treatment-emergent serious adverse events (SAEs), deaths, and TEAEs that led to treatment discontinuation of lenvatinib, pembrolizumab, or both, dose reduction of lenvatinib, or dose interruption of lenvatinib, pembrolizumab, or both will be provided.

The incidence of the following events will be reported as the number (percentage) of subjects with TEAEs by MedDRA SOC and PT:

- TEAEs
- TEAEs by worst CTCAE grade
- TEAEs with worst CTCAE grade 3 or above
- TEAEs with any CTCAE grade 3 or 4
- Treatment-emergent SAEs
- Fatal TEAE
- Non-fatal treatment-emergent SAEs
- Treatment-related TEAEs
- Treatment-related TEAEs by CTCAE grade
- Treatment-related TEAEs with worst CTCAE grade 3 or above
- Treatment-related TEAEs with any CTCAE grade 3 or 4
- Treatment-related treatment-emergent SAEs
- Treatment-related Fatal TEAE
- TEAEs leading to discontinuation of lenvatinib
- TEAEs leading to dose reduction of lenvatinib
- TEAEs leading to dose interruption of lenvatinib
- TEAEs leading to dose modification (reduction/interruption) of lenvatinib
- TEAEs leading to discontinuation of pembrolizumab
- TEAEs leading to dose interruption of pembrolizumab
- TEAEs leading to discontinuation of both lenvatinib and pembrolizumab
- TEAEs leading to dose interruption of both lenvatinib and pembrolizumab

Subject data listings of all deaths, SAEs, AEs leading to death, treatment discontinuation, dose reduction, or dose interruption will be provided. All AE regardless of treatment-emergent or not will be included in the subject data listings.

The following TEAE tables will be provided for clinically significant TEAEs (CSAE) for lenvatinib, and TEAEs of special interest (AEOSI) for pembrolizumab.

- Overview of CSAE for lenvatinib (for overall and respective CSAE group)
- Overview of AEOSI for pembrolizumab (for overall and respective AEOSI group)
- CSAE for lenvatinib by PT and worst CTCAE grade
- AEOSI for pembrolizumab by PT and worst CTCAE grade

5.6.4 Laboratory Values

Laboratory results will be summarized using Système International (SI) units. For all quantitative parameters listed in Protocol Section 9.5.1.5.3, the actual value and the change from baseline to each postbaseline visit will be summarized by visit using summary statistics. Qualitative parameters listed in Protocol Section 9.5.1.5.3 will be summarized by number and percentage of subjects, and changes from baseline to each postbaseline visit will be reported using shift tables. Percentages will be based on the number of subjects with both nonmissing baseline and relevant postbaseline results.

Box and whisker plots will be used to show the longitudinal change of the parameters across visits.

Laboratory test results will be assigned a low/normal/high (LNH) classification according to whether the value is below (L), within (N), or above (H) the laboratory parameter's reference range. The result of LNH classification will be provided in a subject data listing.

Laboratory parameters will be graded by CTCAE ver. 4.03. Changes from CTCAE grade at baseline to worst postbaseline will be reported using shift tables.

CTCAE ver. 4.03 will be used to identify subjects with treatment-emergent markedly abnormal laboratory values (TEMAV). The number (percentage) of subjects with TEMAV (markedly abnormal high/low) will be summarized using worst CTCAE grade for overall study period. The TEMAV is defined in [Section 8.3](#). The number (percentage) of subjects with an increase of at least 1 CTCAE grade from baseline to the worst postbaseline value of any grade will also be presented.

Shifts from baseline to worst postbaseline value for proteinuria determined by dipstick (negative, trace, 1+, 2+, 3+, 4+), and a summary of proteinuria from 24-hr urine collection will be provided.

The frequency and percentage of values \leq the upper limit of normal (ULN) and $>$ ULN of thyroid function test will be summarized at baseline and worst postbaseline value.

Subject data listings will be provided.

5.6.5 Vital Signs

Summary statistics for vital signs parameters (diastolic and systolic blood pressure, pulse, and temperature) and weight, and changes from baseline will be presented by visit.

Hypertension based on vital signs (diastolic and systolic blood pressure) will be presented using shift from baseline to worst postbaseline CTCAE grade. Category of hypertension is defined as [Table 3](#).

Table 3 Hypertension Grades Based on Blood Pressure

Grade	Blood Pressure (mm Hg)
0 (Normal)	Systolic<120 and Diastolic<80
1 (Prehypertension)	Systolic 120 – 139 or Diastolic 80 – 89
2 (Stage 1 Hypertension)	Systolic 140 – 159 or Diastolic 90 – 99
3 (Stage 2 Hypertension)	Systolic \geq 160 or Diastolic \geq 100

Box and whisker plots will be used to show the longitudinal change of the parameters by visit.

Subject data listings will be provided.

5.6.6 Electrocardiograms

The results of ECG assessments performed at each visit will be evaluated. Summary statistics for ECG parameters (Heart Rate, RR, PR, QRS, QT, and QTcF) and changes from baseline will be presented by visit.

Shift tables will present changes from baseline in ECG interpretation (categorized as normal; abnormal, not clinically significant; and abnormal, clinically significant) to each visit.

In addition, the number (percentage) of subjects who met below criteria at least once in QTcF will be presented:

Absolute QTcF interval prolongation:

- QTcF interval >450 ms
- QTcF interval >480 ms
- QTcF interval >500 ms

Change from baseline in QTcF interval:

- QTcF interval increases from baseline >30 ms
- QTcF interval increases from baseline >60 ms

Subject data listings will be provided.

